3.3.5 Discontinuation of patients from treatment or assessment

3.3.5.1 Criteria for discontinuation

Patients may be discontinued from study treatment and assessments at any time. Specific reasons for discontinuing a patient from this study are:

- 1. Voluntary discontinuation by the patient who is at any time free to discontinue his/her participation in the study, without prejudice to further treatment.
- 2. Safety reasons as judged by the investigator, AstraZeneca and/or Bristol-Myers Squibb Pharmacovigilance.
- 3. Severe non-compliance to protocol as judged by the investigator and/or AstraZeneca.
- 4. Incorrect enrolment or randomization, ie, the patient does not meet the required inclusion/exclusion criteria for the study.
- 5. Patient lost to follow-up (as defined by, unable to reach the patient after 3 documented phone calls, fax, e-mail, or attempts to contact him/her through patient

locator agencies (if allowed per national regulation) and having sent one letter by registered/certified mail; all should be documented in the patients medical records).

Study specific discontinuation criteria are listed below. The FPG and HbA1c values will be measured at the central laboratory.

- 6. Use of (need for) any antihyperglycaemic medication other than investigational product or open-label metformin for more than 14 consecutive days, however insulin during hospitalisation is allowed.
- 7. Treatment with chronic systemic glucocorticoids. However, two temporary periods no longer than 7 days each are allowed.
- 8. Severe and/or frequent hypoglycaemic events, defined as ≥ 1 major event or recurring minor events and the possibility of down-titration and contributing factors (eg, excessive physical activity) has been evaluated.
- 9. Patients whose double blind treatment codes are broken by the investigator.
- 10. Pregnancy.
- 11. FPG >15.0 mmol/L (>270 mg/dL) at Visit 4 (Week 3) confirmed at a repeated measurement.
- 12. FPG >13.3 mmol/L (>240 mg/dL) at Visit 7 (Week 12) and on maximum titrated tolerated dose for at least two weeks confirmed at a repeated measurement.
- 13. FPG >12.2 mmol/L (>220 mg/dL) at Visit 9 (Week 18) and on maximum titrated tolerated dose for at least two weeks confirmed at a repeated measurement.
- 14. FPG >11.1 mmol/L (>200 mg/dL) at Visit 10 (Week 24) confirmed at a repeated measurement.
- 15. HbA1c >8.0% at Visit 11 (Week 30) and Visit 12 (Week 39).
- 16. HbA1c >7.5% at Visit 13 (Week 52), Visit 14 (Week 65) and Visit 15 (Week 78).

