- 1. Hypoglycaemic event: the null hypothesis is the equality of the two proportions of patients with at least one hypoglycaemic event against the alternative hypothesis of the inequality of the two proportions of patients with at least one hypoglycaemic event. Fisher's exact test will be used to compare the association of two proportions with the treatment on the safety analysis set.
- 2. Change from baseline to Week 52 in body weight: The null hypothesis is the equality of the two mean weight changes from baseline to Week 52 against the alternative hypothesis of the inequality of the two mean weight changes are not

equal. Analysis of covariance model (ANCOVA) method will be used on safety analysis set, where mean changes from baseline to Week 52 will be the response variable and the model will include treatment as a fixed effect and baseline weight as a covariate.

3. Durability: the null hypothesis is the equality of the two mean slopes against the alternative hypothesis of the inequality of the two slopes. Student's t-test will be use on patients who have HbA1c levels recorded for Week 24 and at least a second one recorded on or before Week 52. Missing values will not be imputed for visits between Week 24 and Week 52.

Other secondary efficacy variables are:

- Change from baseline in FPG, insulin, C-peptide, glucagon and proinsulin.
- Proportion of patients achieving a therapeutic glycaemic response defined as HbA1c ≤6.5%.
- Change from baseline in HbA1c in patients with baseline HbA1c \geq 7.0%.
- Proportion of patients achieving a therapeutic glycaemic response defined as HbA1c < 7.0% in patients whose baseline HbA1c is $\ge 7.0\%$.
- Change from baseline in β -cell function (as measured by HOMA-2 (Wallace et al 2004)).
- Change from baseline in AUC from 0 to 180 minutes for glucose, insulin, C-peptide and glucagon during an OGTT on a subset of patients.
- Change from baseline in insulinogenic index (Phillips et al 1994)) on a subset of patients.
- Change from baseline in insulin sensitivity as measured by OGIS (Mari et al 2001) and Matsuda Index (Matsuda and DeFronzo 1999) on a subset of patients.
- Change from baseline in TC, LDL-C, HDL-C and TG.

Data analysis for population pharmacokinetics will be outlined in a separate analysis plan and the results will be reported in a separate report.

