6.3.3 Per protocol analysis set

For the analysis of Week 52 primary efficacy endpoint and all secondary efficacy endpoints, the PP analysis set is a subset of full analysis set including patients who have completed the 52 weeks of randomized treatment period and have no reasons for exclusions.

These exclusions from the PP analysis set will include but not be limited to the patients who took prohibited concomitant medications, non-compliance to investigational product and major deviations of study procedures. The exclusions from the PP analysis set will be explicitly defined in SAP prior to Week 52 database locking. The non-inferiority conclusion pertaining to the primary endpoint will be drawn primarily based on results from per protocol analysis set and complementally based on full analysis set (see Section 6.3.4).

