Durability of HbA1c will be assessed for each of the two treatment groups from mean slopes of the regressions of change from Week 24 in HbA1c on treatment duration from Week 24 to Week 52. All patients with a pair of HbA1c levels at Week 24 and post Week 24 will be included. Weeks on randomized treatment period will be used as a regressor. Only observed values between the two visits, inclusive, will be used for the analysis.

Three secondary variables (proportion of patients reporting hypoglycaemic events and change from baseline in body weight, and mean slopes of the regressions of change from baseline in HbA1) have been identified for special consideration in this study, in addition to the primary efficacy variable (NI HbA1c). In order to control overall type 1 error rate of the study, a fixed-

sequence test will be adopted with respect to the 4 hypotheses, ie, the testing will be sequentially performed in the following order:

- 1. Non-inferiority comparison of HbA1c, if NI is demonstrated then statistical inference proceed step 2, otherwise inference will stop.
- 2. Superiority tests for hypoglycaemic event if significant (p<0.05) in favour of saxagliptin and metformin treatment group then statistical inference proceed step 3, otherwise inference will stop.
- 3. Superiority test for weight changes, if significant (p<0.05) in favour of saxagliptin and metformin treatment group then statistical inference proceed step (4), otherwise inference will stop.
- 4. Superiority inference for durability.

All comparison will be two-sided at the 5% significance level.

All other secondary efficacy variables are supplemental and not included in the multiple comparison scheme as outlined above.

Summary tables will be presented for proportions of patients achieving glycaemic therapeutic response.

Change from baseline in AUC from 0 to 180 minutes for glucose, insulin, C-peptide and glucagon will be analyzed by ANCOVA method similar for the primary endpoint. The lipid endpoints will be log-transformed before ANCOVA analysis. In which case log baseline will be used as a covariate and treatment as a fixed effect in the model. Within the framework of the ANCOVA model, point estimates and the two-sided 95% confidence intervals will be first constructed in the logarithmic scale. By taking the anti-logarithms, estimates and confidence intervals for the true geometric means and ratios of true geometric means will be displayed.

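### The step-4 durability test gives two-point and full HbA1c slopes equal weight, which costs power, and its analysis set conflicts with section 6.3.3

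*Protocol*

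**What the plan says.** Durability is an efficacy objective (Protocol 2.2) and the last of four hypotheses tested in fixed sequence at two-sided 5% (6.4.1).

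- **Hypothesis (6.2):** "Durability: the null hypothesis is the equality of the two mean slopes against the alternative hypothesis of the inequality of the two slopes".
- **Summary measure (6.4.1):** "Durability of HbA1c will be assessed for each of the two treatment groups from mean slopes of the regressions of change from Week 24", with weeks on treatment as the regressor.
- **Test and minimum data (6.2):** "Student's t-test will be use on patients who have HbA1c levels recorded for Week 24 and at least a second one recorded" by Week 52, without imputation.
- **Patients (6.4.1):** "All patients with a pair of HbA1c levels at Week 24 and post Week 24 will be included".
- **Data (6.4.1):** "Only observed values between the two visits, inclusive, will be used for the analysis".
- **Per protocol set (6.3.3):** "all secondary efficacy endpoints, the PP analysis set is a subset of full analysis set including patients who have completed the 52 weeks". Section 6.3 instead says that only selected secondary efficacy endpoints use this set.
- **Withdrawal inside the slope window (3.3.5.1):** "HbA1c >8.0% at Visit 11 (Week 30) and Visit 12 (Week 39"). Unlike the FPG criteria, this one asks for no repeat measurement.
- **Early termination (3.3.5.2):** patients who stop in Period C should have the Visit 13 procedures, and Table 4 includes HbA1c at that visit.

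The protocol names no weighting and no mixed model for durability. The repeated measures analysis in 6.4.1 is optional and not tied to this endpoint.

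**The concern.** A Student's t-test of mean slopes implies one regression slope per patient, all weighted alike. A slope over six weeks is far noisier than one over 28 weeks, so a modest share of short slopes can dominate the variance of the arm mean.

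The short slopes do not arise purely at random either. Some belong to patients stopped because a single observed HbA1c exceeded 8.0%, which tends to select upward measurement error at the end of the slope. Ordinary dropout supplies the rest.

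The analysis set is also open. The completer set of 6.3.3 and the pair-of-values set of 6.2 and 6.4.1 behave differently, so one confirmatory hypothesis could give two results. Section 6.4.3 reuses the same slope method through Week 104, where the HbA1c withdrawal thresholds fall to 7.5% and then 7.0%.

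**Working it through.** **The plan's own figure.** Section 6.5 gives power only for the primary comparison. With 272 evaluable per arm (544/2), SD 1.1 and margin 0.35, the standard error is 1.1 × √(2/272) = 0.0943, and 0.35/0.0943 − 1.96 = 1.75, so power is 96.0% against the stated 95%. That figure reproduces. No power is stated for durability.

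**Slope precision, from the visit weeks alone.** The error variance of a least-squares slope is σ²/Sxx, where Sxx is the sum of squared deviations of the weeks from their mean.

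| Weeks observed | Sxx | Error variance relative to full slope |
|---|---|---|
| 24, 30, 39, 52 | 444.75 | 1 |
| 24, 30, 39 | 114 | 3.9 |
| 24, 30, 32 (termination sample, timing assumed) | 34.7 | 12.8 |
| 24, 30 | 18 | 24.7 |
| 24, 26 (termination sample, timing assumed) | 2 | 222 |

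**Adding true variation between patients.** The total variance is τ² + σ²/Sxx. Assume τ = 0.01%/week (not in the documents).

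- σ = 0.2: two-point 0.0001 + 0.04/18 = 0.002322; four-point 0.0001 + 0.04/444.75 = 0.000190; ratio 12.2.
- σ = 0.3: two-point 0.0001 + 0.09/18 = 0.005100; four-point 0.0001 + 0.09/444.75 = 0.000302; ratio 16.9.

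**Cost of equal weights, illustrated.** Suppose 10% of patients have two points and 90% have four, with σ = 0.3. The per-patient variance of the unweighted mean is 0.1 × 0.005100 + 0.9 × 0.000302 = 0.000782. With inverse-variance weights it is 1/(0.1/0.005100 + 0.9/0.000302) = 0.000334. The ratio is 2.3.

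**Simulated power.** Assumptions: 340 per arm with Week 24 data, Week 24 mean 7.1% (SD 0.7), τ = 0.01, 3% other dropout per interval, withdrawal at HbA1c above 8.0% at Week 30 or at Week 39, and true slopes 0.004 against 0.008%/week. The random-slope model was given its true covariance, which flatters it slightly.

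| Error SD | Termination sample 2 weeks later | t-test | Random-slope model |
|---|---|---|---|
| 0.2 | no | 0.64 | 0.92-0.93 |
| 0.2 | yes | 0.74 | 0.92 |
| 0.3 | no | 0.35 | 0.74 |
| 0.3 | yes | 0.48 | 0.79 |

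A second simulation at the same slopes, slope SD and error SDs gave, for the t-test against the model, 0.60 v 0.87 and 0.33 v 0.74 without the sample (error SD 0.2 and 0.3), and 0.74 v 0.92 and 0.53 v 0.79 with it. The two agree within about 5 points. The ranges in the conclusion are from the second.

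**Within-arm level.** With a true slope of 0.006 in both arms, the t-test arm means come out at 0.0067-0.0083 (error SD 0.2) and 0.0076-0.0114 (error SD 0.3). The model returns 0.0060.

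**Between-arm bias, with equal true slopes.**

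- Arms at the same HbA1c level: no bias, and rejection stays near 5%.
- Arms 0.2-0.3% apart, no termination sample: bias 0.0007-0.0022%/week, two-sided rejection 7.5-11.6%.
- Arms 0.2-0.3% apart, with the sample: bias 0.0002-0.0006%/week, rejection 5.2-5.8%.

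**The completer set of 6.3.3.** At error SD 0.3 without the sample, the SD of the estimated difference is 0.00152 in completers, 0.00150 for the model and 0.00268 for the t-test on all pairs. Completers' slopes are slightly too low (0.0056 against a true 0.0060). The choice of set therefore changes both precision and level.

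**The case against.** **The early-termination sample.** Patients stopped at Week 30 should still have an HbA1c under the Visit 13 procedures. It is taken after the trigger, so its own error was not selected. This stands: it removes most of the between-arm bias and part of the power loss. It does not remove the rest, because a Week 24/30/32 slope still has 12.8 times the error variance of a full one. Patients stopped under the Week 24 FPG rule could also contribute very short pairs.

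**The bias scenario rarely reaches step 4.** A reader might infer that the test is materially biased against saxagliptin. That needs arms at clearly different HbA1c levels. If saxagliptin were truly 0.3% worse at Week 52, non-inferiority would pass with probability Φ((0.35 − 0.30)/0.0943 − 1.96) = Φ(−1.43), about 8%, and two superiority tests would follow. A milder gap is plausible: zero difference at Week 52 (6.5) with slopes differing by 0.004%/week puts the arms 0.004 × 28 = 0.112% apart at Week 24. That is below the gaps simulated here.

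**Specific text over general.** Sections 6.2 and 6.4.1 define durability's own patients, 6.3 says selected, and 6.4.1 excepts durability from the general approach to secondary endpoints. This reading is reasonable and makes the conflict milder. But 6.3.3 says all and makes no exception, so the text still needs reconciling.

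**The rule's wording.** The 8.0% criterion joins Weeks 30 and 39 with the word and. The simulations apply it at each visit, in line with 3.1, which has the criteria assessed at every maintenance visit. If both values were required, the rule would produce three-point slopes (ratio 3.9) and the loss would be smaller.

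**Conclusion.** The point holds, mainly as a loss of power. Equal weighting of slopes whose error variances differ up to 24.7-fold at scheduled visits follows from the stated test and the visit weeks. Under the assumed variances and true slopes, power is about 0.33-0.60 against 0.74-0.87 without early-termination samples, and about 0.53-0.74 against 0.79-0.92 with them. The variance components, HbA1c levels, dropout and sample timing are assumptions.

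Withdrawal inflates the mean slope within each arm. The comparison between arms is biased only if the arms differ in HbA1c level, and then only slightly when the Visit 13 value is taken and used. The documents do not support the stronger inferences that the test is invalid or that it always loses most of its power. The loss reaches about half only at error SD 0.3 without termination samples.

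The conflict over the analysis set is real but mild, and should be settled first: under 6.3.3 the inefficiency would nearly vanish, replaced by a slight downward selection of completers.

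**What to change.** Make the confirmatory durability analysis a linear mixed model on all observed HbA1c from Week 24 to Week 52, with early-termination values entered at their actual time. Include treatment, week and treatment-by-week as fixed effects and a random intercept and slope per patient. Test treatment-by-week. This weights each patient by the information supplied and allows for withdrawal that depends on observed HbA1c.

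Name one set: all treated randomized patients with a Week 24 value and at least one later value. Add to 6.3.3 that durability is excepted, and align 6.3 with it. Keep the slope t-test as a sensitivity analysis, and carry the change into 6.4.3.

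The cost is wording in the protocol and SAP before unblinding, with no new data. The small downside is reliance on a model-based estimate that is valid under missing at random.

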6.3 Description of analysis sets

The primary outcome and selected secondary efficacy endpoints analyses will be performed on the Per Protocol (PP) analysis sets. All efficacy endpoints will also be analysed using the full analysis sets. The safety endpoints will be analysed from the safety analysis set.

6.3.1 Lead-In analysis set

For the summary of patients enrolled to the lead-in period (Period B), all patients who enrolled to the Period B with an E-code and took at least one placebo dose during the lead-in period will be included in the analysis set.

6.3.2 Randomized analysis set

For the summary of baseline characteristics, all patients with a randomization code will be included in the analysis set.

6.3.3 Per protocol analysis set

For the analysis of Week 52 primary efficacy endpoint and all secondary efficacy endpoints, the PP analysis set is a subset of full analysis set including patients who have completed the 52 weeks of randomized treatment period and have no reasons for exclusions.

These exclusions from the PP analysis set will include but not be limited to the patients who took prohibited concomitant medications, non-compliance to investigational product and major deviations of study procedures. The exclusions from the PP analysis set will be explicitly defined in SAP prior to Week 52 database locking. The non-inferiority conclusion pertaining to the primary endpoint will be drawn primarily based on results from per protocol analysis set and complementally based on full analysis set (see Section 6.3.4).

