6.3.4 Full analysis set last observation carried forward (LOCF)

For the analysis of all Week 52 efficacy endpoints, the full analysis set is a subset of randomized analysis set including patients who take at least one randomized investigational product dose, have non-missing baseline and a post baseline efficacy data. The missing Week 52 efficacy endpoints will be replaced by last observed value after baseline. Missing baseline (Visit 3) data will be estimated by a single value assessed at Visit 1, if one exists. Analysis of efficacy variables at Week 52 will be supplemented by the results from the full analysis set.

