6.4 Method of statistical analysis

6.4.1 Analysis of double-blind treatment Period C

The primary efficacy analysis to establish non-inferiority with 0.35% non-inferiority limit on the change in HbA1c from baseline to Week 52 will be performed on a per protocol analysis set using ANCOVA. The model will use treatment group as a fixed effect and baseline value as a covariate. Within the framework of the ANCOVA model, point estimates and the two-sided 95% confidence intervals for the mean change within each treatment group as well as for the differences in mean change between the saxagliptin plus metformin treatment arm and the glipizide plus metformin treatment arm will be performed. Saxagliptin plus metformin will be considered not inferior to glipizide plus metformin if the upper limit of the two-sided 95% confidence interval of the difference in change in HbA1c from baseline to Week 52 between saxagliptin plus metformin and glipizide plus metformin is less than 0.35%.

Analyses of the secondary efficacy endpoints will be performed using ANCOVA methods for change from baseline in glucose related endpoints, β -cell functions, and insulin sensitivity. The ANCOVA model will use treatment group as a fixed effect and baseline value as a covariate. Within the framework of the ANCOVA model, point estimates and the two-sided 95% confidence intervals for the mean change within each treatment group as well as for the differences in mean change between the two treatment groups will be reported.

Repeated measures analysis may be performed on selected efficacy variables over time as sensitivity analysis.

Hypoglycaemic events and body weight changes are considered as safety variables and are specified as important secondary variables supporting the treatment of saxagliptin. Proportion of patients reporting at least one episode of hypoglycaemic event over the 52-week treatment period will be compared between the two treatment groups using a two-sided Fisher's exact test. ANCOVA method comparing the two treatment groups will be used for change from baseline in body weight at Week 52, where the model will include treatment as a fixed effect and baseline as a covariate.

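### The primary non-inferiority test keeps only 52-week completers although poor glycaemic control is itself a ground for withdrawal, so if saxagliptin is truly worse the estimated difference shrinks and the 2.5% error is exceeded

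*Protocol*

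**What the plan says.** Section 6.3.3 states that "the PP analysis set is a subset of full analysis set including patients who have completed the 52 weeks of randomized treatment period" with no reason for exclusion. Further exclusion reasons are left to the SAP; the completion requirement is not. Under section 6.4.1 the primary analysis "will be performed on a per protocol analysis set using ANCOVA". Section 6.3.3 says the conclusion is "drawn primarily based on results from per protocol analysis set and complementally based on full analysis set".

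Section 3.3.5.1 lists the glycaemic grounds for discontinuation before Week 52. Criteria 11 to 14 are FPG limits at Weeks 3, 12, 18 and 24, the last being "FPG >11.1 mmol/L (>200 mg/dL) at Visit 10 (Week 24) confirmed at a repeated measurement". Criterion 15 is "HbA1c >8.0% at Visit 11 (Week 30) and Visit 12 (Week 39").

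The full analysis set (section 6.3.4) keeps these patients: "The missing Week 52 efficacy endpoints will be replaced by last observed value after baseline". Section 3.3.5.2 asks patients who stop in Period C to complete the Visit 13 procedures, so a value at withdrawal should exist.

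Step 1 of the fixed sequence in section 6.4.1 opens the three superiority tests once non-inferiority is shown. It does not require the full analysis set to meet the 0.35% limit.

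**The concern.** A per protocol set is normally chosen in a non-inferiority trial because non-adherence dilutes a real difference. Here part of the removal is triggered by glycaemic response. Criterion 15 acts on HbA1c, the primary variable, and the FPG criteria act on a closely related measure. A patient withdrawn at Week 30 or 39 for HbA1c above 8.0% has not completed 52 weeks and cannot enter the primary analysis.

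If the treatments are equally effective, both arms lose similar patients. If saxagliptin is worse, its arm loses more failures, the remaining arms look more alike, and the estimated deficit is too small. That is the situation in which the one-sided 2.5% error must hold. Step 1 also opens the tests on hypoglycaemia, weight and durability, so the control of error across all four hypotheses rests on it.

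**Working it through.** **1. The plan's own figure.** Section 6.5 gives SD 1.1%, margin 0.35%, true difference 0, 838 randomized and about 35% outside the PP set. 838 × 0.65 = 544.7, matching the stated 544, or 272 per arm.

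SE = 1.1 × √(2/272) = 0.0943. Power = Φ(0.35/0.0943 − 1.96) = Φ(1.75) = 96.0%.

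The stated 95% is reproduced. The sample size is not in question.

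**2. What shrinkage does to the error.** Non-inferiority is declared when the estimate + 1.96 SE is below 0.35. If the expected estimate is E, the probability is Φ((0.35 − E)/SE − 1.96). At a true difference of 0.35, with SE 0.0943:

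- E = 0.35 (no selection): Φ(−1.96) = 2.5%
- E = 0.29: Φ(0.64 − 1.96) = Φ(−1.32) = 9%
- E = 0.25: Φ(1.06 − 1.96) = Φ(−0.90) = 18%
- E = 0.19: Φ(1.70 − 1.96) = Φ(−0.26) = 40%

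**3. How far E shrinks.** Simulation with 419 per arm and 1,500 trials per row; ANCOVA on change with treatment and baseline.

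- From the protocol: SD of change 1.1% (6.5) and a glipizide change of −0.6% (the assay-sensitivity figure in 6.2).
- Assumed, because the protocol does not give them: baseline mean 7.5 or 7.7% and SD 0.9%, correlation between visits 0.6 or 0.8, slope of change on baseline −0.4, and 15% other exclusions at random.
- Only criterion 15 was applied, read once as either visit and once as both. The FPG criteria were not simulated.

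True difference 0.35%:

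| Criterion 15 | Corr. | Baseline mean | Withdrawn, glip / saxa | Completers analysed | Completer estimate | False NI | LOCF estimate | False NI, LOCF |
|---|---|---|---|---|---|---|---|---|
| either | 0.6 | 7.5 | 25.5% / 36.7% | 491 | 0.247 | 23.4% | 0.390 | 0.9% |
| either | 0.6 | 7.7 | 31.7% / 43.6% | 444 | 0.233 | 25.9% | 0.379 | 1.1% |
| either | 0.8 | 7.5 | 23.2% / 33.5% | 511 | 0.227 | 33.1% | 0.370 | 0.9% |
| either | 0.8 | 7.7 | 28.9% / 40.2% | 466 | 0.216 | 37.0% | 0.368 | 1.7% |
| both | 0.6 | 7.5 | 9.2% / 15.7% | 623 | 0.290 | 11.1% | 0.366 | 1.7% |
| both | 0.6 | 7.7 | 12.6% / 20.5% | 595 | 0.278 | 15.5% | 0.369 | 1.9% |
| both | 0.8 | 7.5 | 11.6% / 18.8% | 604 | 0.262 | 20.4% | 0.359 | 1.4% |
| both | 0.8 | 7.7 | 15.5% / 23.8% | 572 | 0.246 | 25.7% | 0.354 | 1.6% |

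Keeping every simulated patient's Week 52 value gave 0.344 to 0.352 and false rates averaging 2.6%, so the excess comes from the selection. Repeat simulations of the same design widened the completer range to 0.19-0.29 and 11-48%; LOCF gave 0.4% to 2.6%.

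**4. Other true differences.** At zero, the completer estimate was within 0.003 of zero in all eight settings. With saxagliptin better by 0.20 (either visit, correlation 0.8, baseline mean 7.7) it was −0.13, again closer to zero.

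**5. Why both sets.** In one contrived case saxagliptin had fewer withdrawals at Weeks 30/39 (24% against 29%) yet was worse by 0.35 at Week 52. Completers then gave 0.41 (false rate 0.3%) and LOCF 0.22 (46.7%). Replacing one set by the other is therefore no safeguard in general; requiring both is safer.

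**The case against.** The strongest reply is that the protocol already has the protective analysis. LOCF on the full set is prespecified, retains the failures and holds the error in the settings above, so a discrepancy between the sets would be visible. That stands: what is missing is a decision rule, not an analysis. But the protocol does not say what follows if the PP set passes and the full set fails, and it calls the PP set primary.

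The size is also open to challenge. It rests on assumptions the protocol does not give. Under the either-visit reading, criterion 15 alone removes 34-44% of the saxagliptin arm, about as much as or more than the whole 35% allowance in section 6.5. Under the both-visit reading the table gives 11-26%. That is smaller but still at least four times nominal.

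Several stronger readings are tempting but not supported:

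- **That the analysis always favours non-inferiority.** The bias is toward zero. It is absent at the planning assumption of no difference and works against saxagliptin if saxagliptin is better.
- **That all the withdrawal limits act on the primary variable.** FPG is not the primary variable; before Week 52 only criterion 15 uses HbA1c.
- **That hypoglycaemia withdrawals add a known further bias.** Criterion 8 covers "Severe and/or frequent hypoglycaemic events, defined as ≥ 1 major event or recurring minor events", but the protocol gives no expected rate and does not say these patients have the lowest HbA1c. It also requires that down-titration be considered first. The effect ranges from little to large depending on who is assumed to leave, so no figure is offered.
- **That the secondary results share the fault to the same degree.** Responder proportions are only summarised, other secondary efficacy variables are outside the testing scheme, and all efficacy endpoints are also analysed on the full set. Hypoglycaemia and weight use the safety set. Durability uses patients with a Week 24 value and a later one.

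**Conclusion.** The concern holds in conditional form. Completion as an entry condition, together with withdrawal for poor glycaemic control, makes the primary set depend on response. When saxagliptin is truly worse by the margin, the chance of wrongly declaring non-inferiority rises from 2.5% to somewhere between about 11% and 48%. The exact figure depends on baseline level, visit correlation, other exclusions and the reading of criterion 15, and should be taken as illustrative. In the table the lowest rate is already above four times nominal, under either reading of the criterion. The direction reverses only if withdrawals at Weeks 30 and 39 run against the ordering at Week 52. Because this affects the primary conclusion and the gate for the key secondary claims, it should be corrected before unblinding.

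**What to change.** In section 6.3.3 and in step 1 of the sequence in section 6.4.1, state that non-inferiority is declared only if the upper limit of the two-sided 95% interval is below 0.35% in both the PP set and the full analysis set. In section 6.3.4, specify that patients withdrawn early contribute their last on-treatment HbA1c, including the value from the withdrawal visit. The repeated-measures analysis that section 6.4.1 leaves optional can serve as sensitivity, using all on-treatment HbA1c values.

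The PP set can stay as defined, and the withdrawal rules need not change. The sponsor should clarify whether criterion 15 means either visit or both, since this alters how many patients leave; this review takes no view on which is right.

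Cost: protocol and SAP wording only, because the data are already scheduled for collection. There is a second condition to pass, but at zero true difference about 97% to 99% of simulated trials pass both.
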